12 SUPPORTING DOCUMENTATION AND OPERATIONAL CONSIDERATIONS	27
12.1 Regulatory, Ethical, and Study Oversight Considerations	27
12.1.1 Informed Consent Process	27
12.1.1.1 Quality improvement strategy delivery	27
12.1.1.2 Patient phone survey	27
12.1.1.7 Chart Review for Randomized Participants	28
12.2 Confidentiality and Privacy	28
12.2.1 Future Use of Stored Specimens and Data	28
12.2.2 Data sharing	28
12.3 Safety Oversight	28

12.4 Key Roles and Study Governance	28
12.5 Clinical Monitoring	29
12.6 Data Handling and Record Keeping	29
12.7 Data Collection and Management Responsibilities	29
12.8 Study Records Retention	29
12.9 Protocol Deviations	29
13 DATA SAFETY MONITORING PLAN	30
13.1 Study Leadership Roster	31
13.2 Protocol Amendment Procedures and Approvals	33
13.3 Clinical Trial Registry and Publication Policy	33
14 APPENDICES	33
14.1 Appendix 1. Criteria for determining appropriateness of antiplatelet therapy.	33
15 ABBREVIATIONS AND SPECIAL TERMS	37
16 REFERENCES	38

AMENDMENTS

Date	Version	Section(s)	Changes
8/4/2022	V.1.1	1.1 1.2 1.3 2.2 4 7.3 8.1 8.2 8.3 9.1 9.2 9.3 11.5	Updated trial timeline to reflect that CNNF follow-up will be delivered to non-responders 2 weeks rather than 4 weeks after delivery of the initial CNNF notification, and patient calls will thus be moved up from week 9-10 to week 7-8 to ensure patient recall of medication use will not be impacted due to too much time passing between delivery of the CNNF strategy and the phone assessment. The amendment also clarifies that CNNF will be delivered to up to 4 patients each week per anticoagulation nurse. While the total number of participants will not change, this may result in the randomized trial lasting for more than the originally stated 25 weeks.
10/27/2022	V.1.2	1.1 1.2 1.3 2.2 4 5.4 7.2 7.3 8.1 8.2 8.3 9.2 9.3 11.5	Updated trial timeline to reflect extension of timing for chart review and patient phone assessments from week 7-8 to week 7-9.
11/30/2022	V.1.3	1.1 1.2 1.3 2.2 4 5.4 7.2 7.3 8.1 8.2 8.3	Updated trial timeline to reflect extension of timing for chart review and patient phone assessments from week 7-9 to week 7-10.

		9.2 9.3 11.5	
12/13/2022	V.1.4	7.3	Updated protocol to reflect that while we will attempt to have blinded research staff conduct all patient phone calls, unblinded staff will assist with calls if necessary to complete all assessments within the specified time window of week 7-10 of study participation.

STATEMENT OF COMPLIANCE

The trial will be conducted in accordance with research best practices, applicable United States Code of Federal Regulation, and the terms and conditions of the sponsor. The Principal Investigator will assure that no deviation from, or changes to the protocol will take place without documented approval from the Institutional Review Board (IRB), except where necessary to eliminate an immediate hazard(s) to the trial participants. All research personnel involved in the conduct of this study have completed Human Subjects Protection and research best practices training.

1 PROTOCOL SUMMARY

1.1 Synopsis

Title:	Anticoagulation with Enhanced Gastrointestinal Safety (AEGIS): A pragmatic randomized trial to evaluate clinician outreach to reduce upper gastrointestinal bleeding risk in patients taking warfarin and antiplatelet therapy
Grant Number:	K23 DK118179
Background	
Patients who use an anticoagulant together with an antiplatelet drug (anticoagulant-antiplatelet therapy or AAT) are at increased risk for serious bleeding, which most commonly occurs in the gastrointestinal tract. For patients on AAT, there are two evidence-based medication optimization strategies to reduce upper gastrointestinal (GI) bleeding risk. Many of these patients may safely discontinue the antiplatelet drug. For patients who must continue the antiplatelet drug, proton pump inhibitors (PPIs) effectively reduce upper GI bleeding risk. Both strategies are underused. The aim of this trial is to evaluate the effectiveness of a novel clinician-facing quality improvement implementation strategy to optimize the use of antiplatelet therapy and PPI gastropreservation for patients who use warfarin and are followed by the Michigan Medicine anticoagulation monitoring service, as part of a quality improvement initiative.

Study Population:	
Clinicians will be eligible for receipt of the implementation strategy if they care for patients who are enrolled with the anticoagulation monitoring service. Patients will be eligible for inclusion if they are prescribed warfarin and an antiplatelet drug without a PPI and are enrolled in the Michigan Medicine anticoagulation monitoring service. See section 6.1 for additional inclusion and exclusion criteria. We anticipate including 220 patients and 110 clinicians.

Study Description:

The study is designed as a pragmatic cluster randomized quality improvement trial. For each patient, a target clinician will be identified, defined as either a cardiologist at Michigan Medicine, if the patient has seen one in the past year, or else the patient's primary care provider if within Michigan Medicine, or else the clinician of record on file with the anticoagulation service. For each patient, assignment to receipt of the quality improvement strategy vs. usual care will be done at the cluster level according to the identity of the target clinician. Each clinician (cluster) will be randomized 1:1 to receive either clinician notification with nurse facilitation (CNNF), consisting of a notification message sent in the electronic health record, or to a usual care arm. Each clinician cluster will be limited to 4 or fewer patients. Following delivery of the quality improvement (QI) strategy to clinicians in the CNNF arm, the study team will conduct phone surveys with all patients whose clinicians received usual care or CNNF and perform chart review in the medical record to evaluate the effect of CNNF on reducing upper GI bleeding risk through discontinuation of all antiplatelet drugs or initiation of PPI co-therapy.

Primary Objective: To determine the extent to which clinician notification with nurse facilitation (CNNF) versus usual care is associated with differences in the proportion of patients who have medication optimization (defined as either discontinuation of all antiplatelet drugs or initiation and adherence to a PPI) at week 7-10.

Secondary Objectives: To determine the extent to which CNNF (vs usual care) is associated with differences in the proportion of patients who are recommended to have medication optimization based on chart review after 6 weeks.

Endpoints*:

Primary Endpoint: The proportion of patients who self-report either discontinuing all antiplatelet therapy (defined as none in the past 7 days) or initiation and adherence to a proton pump inhibitor (defined as use for at least 5 of the prior 7 days) at week 7-10.

Secondary Endpoints:

[figure not shown]
- The proportion of patients with a documented recommendation in the electronic health record to either discontinue all antiplatelet therapy or initiate a PPI

Phase or Stage:

Randomized quality improvement project with a wait-list control group

Description of Sites/Facilities Enrolling Participants:	Participants will be included from a single site (the Michigan Medicine anticoagulation monitoring service in Ann Arbor, Michigan, USA).
Description of Study Intervention/Experimental Manipulation:	
1. Clinician Notification with Nurse Facilitation: A protocol-driven QI strategy in which an anticoagulation clinic nurse sends a templated message to the patient's target clinician that identifies the patient as high risk for upper GI bleeding and summarizes options for medication optimization. In addition, once clinicians decide on a medication optimization plan, the nurse will facilitate execution of the plan and communicate recommendations to the patient.2. Usual Care: No additional education or clinical assistance outside of routine anticoagulation monitoring service care will be included.
Assessments	The only live patient assessment will be a phone survey at week 7-10. Endpoints will also be assessed by chart review.
Human subject's protection:	A waiver of informed consent will be sought for delivery of the clinician notifications, as well as for the patient phone survey, since they constitute minimal risk, the waiver will not adversely affect the rights or welfare of participants, and the research could not practically be carried out otherwise.
Study Duration:	~25 weeks
Participant Duration:	10 weeks

1.2 Schema

1.3 Schedule of Activities

It is anticipated that 110 clinicians will be included in the study, and 220 patients who are cared for by those clinicians. QI strategies will be delivered to clinicians of eligible patients by

anticoagulation clinic nursing staff. Up to 50-56 patients will enter the study each week for 5 weeks (or longer if fewer patients enter each week).

For informational purposes, whether the evaluation vs. the anticoagulation clinic staff performs the activity is indicated in bold. Failure of the anticoagulation clinic staff to follow the clinical protocols for delivery of the clinician- level QI strategies will not be considered study deviations.

Schedule of Activities

Activity	Screening and randomization	Week 1	Week 2-5	Week 7-10	Week 11-25
Eligibility determination of clinicians and patients (research team)	X				
Cluster randomization of patients to CNNF vs. usual care (research team)	X				
Clinician delivery of CNNF for patients randomized to receive it (anticoagulation clinic staff)		X	X		
Additional outreach, communication, or facilitation steps for patients and clinicians as per anticoagulation clinic protocol for CNNF recipients (anticoagulation clinic staff)		X	X		
Patient phone survey, with waiver of informed consent (research team)				X	
Chart review to ascertain exploratory outcomes (research team)	X	X		X	X

2 INTRODUCTION

2.1 Study Rationale & Background

Increasing numbers of patients in the United States are prescribed oral anticoagulants to treat or prevent a range of thromboembolic conditions ¹. The main risk with anticoagulants is major bleeding, most commonly from the gastrointestinal tract ^{2,3}. Many patients prescribed anticoagulants are co-prescribed an antiplatelet drug (aspirin or a thienopyridine), and these patients are at particularly high risk for major bleeding. In an observational study of patients prescribed warfarin, use of an antiplatelet drug increased the risk of major bleeding (5.7% vs. 3.3%), emergency department visits for bleeding (13.3% vs. 9.8%), and hospitalizations for bleeding (8.1% vs. 4.1%), but did not reduce the rate of thrombosis ⁴.

Medication optimization can substantially reduce bleeding risk for patients prescribed anticoagulant-antiplatelet therapy (AAT). One evidence-based practice is to discontinue antiplatelet therapy in patients for whom it is inappropriate. Based on recent clinical trial data, the indications for AAT are increasingly narrow, and most patients prescribed anticoagulants should only use antiplatelet drugs for a limited time after acute coronary syndrome, coronary stenting, or other vascular procedures ⁵. A second evidence-based practice is the use of a proton pump inhibitor (PPI gastroprotection) for patients in whom AAT is truly indicated, a strategy recommended by professional guidelines ^{5,6}. A meta-analysis showed PPIs reduce the risk of UGIB by up to 79% in patients using aspirin or non-steroidal anti-inflammatory drugs ⁷. Both of these evidence-based practices are underused ⁸. In an observational study of six anticoagulation clinics, 45% of patients prescribed warfarin were co-prescribed an antiplatelet drug. Of these, 44% had no identifiable indication for antiplatelet therapy, and 36% were appropriately prescribed AAT but without a PPI ⁸.

There are multiple barriers to use of these evidence-based practices. Clinicians may lack knowledge of appropriate use of medication optimization strategies, have inadequate time or prioritization, or lack “ownership,” since many patients are co-managed by a PCP and a subspecialist (typically a cardiologist) ⁹. In many cases, a clinician may be prepared to assess use of one of the evidence-based practices but not the other, which may lead to suboptimal care. Clinicians may also have concerns about provoking a cardiovascular event when deprescribing antiplatelet drugs, and about possible PPI adverse effects when initiating a PPI ¹⁰.

There is a critical need for implementation strategies to improve medication optimization for upper GI bleeding risk reduction in patients prescribed AAT. Importantly, to ensure the most appropriate care, any implementation strategy should simultaneously address both evidence-based practices, determining first the appropriateness of antiplatelet therapy, then of PPI gastroprotection. Previous one- or two- component clinician-facing interventions aimed at improving use of PPI gastroprotection (including decision support tools, electronic alerts, audit and feedback, and clinician education) have had limited success ¹¹⁻¹³. Several European studies that have tested multi-component interventions involving professional education, incentive payments, clinician feedback, and pharmacist support have effectively reduced the proportion of high-risk patients without gastroprotection (odds ratios 0.55-0.72) ¹⁴⁻¹⁶. However, such

multicomponent strategies are resource intensive and challenging to implement in the fragmented US healthcare system.

As part of a quality improvement program through the Michigan Medicine anticoagulation service, a novel clinician-facing strategy has been identified to improve the safety of patients using AAT: clinician notification by electronic health record (EHR) message including a multi-faceted nurse facilitated process. The anticoagulation clinic has recently completed a pilot feasibility study that confirmed that delivery of the implementation strategy was feasible, that the strategy was acceptable to clinicians and patients, and that completing the necessary steps for the project did not impair the anticoagulation clinic nurses ability to perform other duties. In the pilot study, feedback was elicited from patient, clinician, and nursing staff participants through qualitative semi-structured phone questionnaires. The data from these interviews were used to optimize the implementation strategy and methodology described in this protocol. This protocol describes a randomized evaluation of a quality improvement initiative to determine the effectiveness of this novel clinician-facing approach to improve medication optimization.

2.2 Objectives

Primary Objective: To determine the extent to which clinician notification with nurse facilitation (CNNF) versus usual care is associated with differences in the proportion of patients who have medication optimization (defined as either discontinuation of all antiplatelet drugs or initiation and adherence to a PPI based on self-report) at week 7-10.

Secondary Objectives: To determine the extent to which CNNF (vs usual care) is associated with differences in the proportion of patients who are recommended to have medication optimization based on chart review after 6 weeks.

3 RISK/BENEFIT ASSESSMENT

3.1 Known Potential Risks to Patients

No novel therapeutic medications or devices are being tested in this study and participants are not required to discontinue an antiplatelet agent, initiate a PPI, or make any other medication changes as part of study participation. The risks and benefits discussed here relate to the implementation strategy and assessments of the implementation strategy, but not any possible medication changes undertaken by their clinicians, which are done as part of usual clinical care.

1. **Inconvenience.** Participants may feel inconvenienced by the attempts to reach them, or the time it takes to engage in study phone surveys.
2. **Breach of Data Confidentiality.** It is possible that the identity of the participant or protected health information (PHI) could be unintentionally revealed to persons outside of the research team. As this study does not deal with sensitive or stigmatized behavior

(i.e., illicit drug use), a potential data breach is anticipated to cause minimal harm to the participant if it were to occur.

3.2 Known Potential Risks to Clinicians

1. **Potential Psychological Discomfort due to Subject Content.** The clinician messages will deal with the topic of clinical care practices, including opportunities for clinical care improvement. This could cause clinicians to be upset or concerned. All efforts will be made to discuss these topics in a considerate manner.
2. **Inconvenience.** Clinician participants may feel inconvenienced by the attempts to reach them or the time it takes to engage with communications from anticoagulation clinic staff.
3. **Breach of Data Confidentiality.** It is possible that the identity of the participant could be unintentionally revealed to persons outside of the research team. However, no PHI will be sought from clinicians. As this study does not deal with sensitive or stigmatized behavior (i.e., illicit drug use), a potential data breach is anticipated to cause minimal harm to the participant if it were to occur.

3.3 Assessment of Potential Risks and Benefits

The risks to patients and clinicians are all minimal and justified by the value of the potential benefits and knowledge gained. Risks of confidentiality breach will be mitigated by separation of personal identifiers (enrollment forms) from data source documents. All data source documents and any personally identifying information for trial participants will be stored on a secure drive or in a locked file cabinet and will be accessible only to the study team.

4 OBJECTIVES AND ENDPOINTS

OBJECTIVES	ENDPOINTS
Primary	
To determine the extent to which clinician notification with nurse facilitation (CNNF) versus usual care is associated with differences in the proportion of patients who have medication optimization (defined as either discontinuation of all antiplatelet drugs or initiation and adherence to a PPI based on self-report) at week 7-10.	The proportion of patients who self-report either discontinuing all antiplatelet therapy (defined as none in the past 7 days) or initiating and adhering to a proton pump inhibitor (defined as use for at least 5 of the prior 7 days) at week 7-10.
Secondary	

To determine the extent to which CNNF (vs usual care) is associated with differences in the proportion of patients who are recommended to have medication optimization based on chart review after 6 weeks.	The proportion of patients with a documented recommendation in the electronic health record to either discontinue all antiplatelet therapy or initiate a PPI
Exploratory	
To determine how often the anticoagulation clinic nurse communicated the recommendation to either discontinue all antiplatelet therapy or start a PPI for patients who were randomized to receive CNNF.	The proportion of patients for whom an anticoagulation clinic RN documented communicating a recommendation to the patient to either discontinue all antiplatelet therapy or start a PPI based on chart review.
To determine how often the anticoagulation clinic nurse pended an order for a PPI for patients randomized to CNNF and recommended by their clinician to initiate PPI.	The proportion of patients for whom an anticoagulation clinic RN pended an order for a PPI among patients randomized to CNNF and recommended by their clinician to initiate PPI.
To explore why patients recommended to either discontinue an antiplatelet drug or initiate a PPI may choose not to make the medication change.	The reasons why patients who received a recommendation to make a medication change chose not to adhere to the recommendation according to patient self-report at week 7-10 (qualitative).
To explore the accuracy of the electronic health record's medication list for PPIs and antiplatelet drugs at baseline.	
The proportion of patients who, retrospectively, report that they had been using antiplatelet therapy at baseline during the patient phone survey at week 7-10.
 
The proportion of randomized patients who, retrospectively, report that they had been using PPI at baseline during the patient phone survey at week 7-10.

To explore the accuracy of the electronic health record's medication list for PPIs and antiplatelet drugs at week 7-10.	
The accuracy of the EHR medication list at week 7-10 for antiplatelet drugs compared to self-report.
 
The accuracy of the EHR medication list at week 7-10 for proton pump inhibitors compared to self-report.

To explore the appropriateness of antiplatelet therapy used by patients at the time of study entry.	The clinical appropriateness of baseline antiplatelet therapy as determined by a physician reviewing the medical record. Antiplatelet appropriateness will be categorized as probably guideline concordant, probably not guideline concordant, or uncertain in reference to

	practice recommendations (Appendix 1). Baseline antiplatelet therapy will be ascertained by self-report at week 7-10.
To explore the extent to which CNNF (vs. usual care) is associated with the appropriateness of antiplatelet therapy at week 7-10.	
The clinical appropriateness of antiplatelet therapy at week 7-10 (relative to appropriateness assessment at the time of study entry, as determined by a physician reviewing the medical record). Antiplatelet appropriateness will be categorized as probably guideline concordant, probably not guideline concordant, or uncertain in reference to practice recommendations (Appendix 1). Antiplatelet therapy at week 7-10 will be determined by patient self-report.
 
We will also evaluate this endpoint for the subset of patients who were recommended to make a medication change.

To explore fidelity to the CNNF vs. usual care	
Fidelity to CNNF will be determined by performing a chart review on patients whose clinicians received the CNNF strategy, to confirm that it was delivered as intended.
 
We will also perform chart review for patients randomized to usual care to ensure that they did not receive CNNF.

To explore patient and clinician factor associated with successful medication optimization.	Regression analysis will be used to identify patient and clinician factors associated with successful medication optimization.
To determine the extent to which CNNF (vs usual care) is associated with differences in the proportion of patients who exhibit PPI adherence, based on self-report, at week 7-10 among patients recommended to start a PPI.	Among patients recommended by a clinician to initiate a PPI (based on chart review at week 7-10), the proportion of days out of the prior 7 when a PPI was taken based on self-report

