7 STUDY IMPLEMENTATION STRATEGIES

7.1 Quality Improvement Strategy Descriptions

The clinician notification process has been formalized as a clinical protocol approved by the anticoagulation clinic to address upper GI bleeding risk. As part of routine care, the QI strategy will be delivered by the anticoagulation nurses assigned to each of 7 anticoagulation clinic teams.

Clinician Notification (CNNF): An anticoagulation clinic nurse sends a templated message to the patient's target clinician that identifies the patient as high risk for upper GI bleeding, summarizes guidelines on appropriate antiplatelet drug use and PPI gastroprotection, and recommends that the clinician consider either discontinuing the patient's antiplatelet drug or initiating a PPI for gastroprotection. The nurse will also offer to pend the order for a PPI if the clinician wants to initiate a PPI and will provide education to the patient on any medication changes recommended by the clinician.

Usual care: With usual care, the anticoagulation clinic will not send the clinician notification letter or other project-specific materials to the clinician or patient.

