7.3 Measures to Minimize Bias: Randomization and Blinding

Assignment of clinicians to CNNF vs. usual care will be done at the cluster level according to the identity of the clinician to be contacted. Clinicians will be stratified by treating small vs. large numbers of patients eligible for the trial, and by procedural vs. non-procedural specialist. The cluster of patients cared for by each anticoagulation clinic target clinician will be randomized 1:1 to get either clinician notification with nurse facilitation (CNNF) or usual care. Randomization will be carried out by the study statistician. For each included clinician, up to 4 patients will be included in their cluster (see section 11.1 for justification). For clinicians with more than 4 eligible patients in their cluster, 4 patients will be selected at random.

Neither patients, clinicians, or anticoagulation staff can practically be blinded. We will attempt to blind the research staff who are making patient calls at week 7-10 to the randomization group of the patient by not providing them with any information that would allow them to infer the randomization group, by not having them enter MiChart for the patients, where such information could be obtained, and by excluding any information from the call script that might help identify the randomization group. However, if due to staffing or personnel issues, blinded research staff are unable to complete all calls within the specified time frame, unblinded research staff will assist with completing patient calls.

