9.3 Assessment of the Secondary and Exploratory Endpoints

The secondary and exploratory endpoints outlined in section 4 of this protocol document will be determined based on chart review, as well as patient self-reported data from the week 7-10 phone survey.

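### Does the secondary endpoint need changing because it does not say whose recommendation counts, when it must be recorded, or whether chart abstractors are masked?

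*Combined protocol and SAP*

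**What the plan says.** Section 4 (repeated in the synopsis, 1.1) defines the secondary endpoint as "The proportion of patients with a documented recommendation in the electronic health record to either discontinue all antiplatelet therapy or initiate a PPI". The paired objective, in 1.1, 2.2 and 4, concerns patients "who are recommended to have medication optimization based on chart review after 6 weeks". Neither gives an author for the recommendation or a start and end date for recording it.

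Other text bears on both questions:

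- The synopsis describes the sequence in the intervention arm: "once clinicians decide on a medication optimization plan, the nurse will facilitate execution of the plan".
- An exploratory PPI-adherence endpoint in section 4 is worded "Among patients recommended by a clinician to initiate a PPI (based on chart review at week 7-10").
- Section 7.1 says the templated message "recommends that the clinician consider either discontinuing" the antiplatelet drug or starting a PPI.
- The schedule in 1.3 has a row "Chart review to ascertain exploratory outcomes (research team"), marked at screening, week 1, week 7-10 and week 11-25.
- Section 9.3 states: "The secondary and exploratory endpoints outlined in section 4 of this protocol document will be determined based on chart review", together with survey data.
- Section 7.3 tries to keep phone callers unaware of the arm, among other means "by not having them enter MiChart for the patients, where such information could be obtained". It does not mention chart abstractors.

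**The concern.** This endpoint is compared between arms by intention to treat (11.2, 11.6), and it is read from the same record that holds the intervention. The CNNF message goes through the electronic record, nurses are trained to document its delivery there (7.2.1), and it names the endpoint's own two options. Usual care has no such message. If an abstractor took any documented suggestion as a recommendation, delivering the intervention would itself score the endpoint, and the arms would differ by construction.

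Three further features add to the worry. The objective's timing has no upper limit, while chart review is also marked for weeks 11-25 and wait-list controls eventually receive CNNF (5.2). The schedule label seems to leave the secondary endpoint without a data source. And the plan accepts that the chart can reveal the arm, yet describes masking only for the callers.

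**Working it through.** **Whose recommendation.** Section 4 sets out a chain of events and measures the steps separately:

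| Step | Where it is measured |
|---|---|
| Message delivered as intended | Exploratory: fidelity |
| Recommendation made | Secondary endpoint |
| Nurse tells the patient | Exploratory: nurse communication |
| Nurse pends a PPI order, among those whose clinician recommended a PPI | Exploratory: order pending |
| Patient has changed medication | Primary endpoint, by phone |

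The secondary endpoint fits the clinician's decision. The order-pending and adherence endpoints both name the clinician as recommender. Section 7.1 has the nurse educate the patient on changes the clinician recommends, and section 10 leaves drug-treatment decisions to the patient's own clinicians. The message asks the clinician to consider two options and recommends nothing to a patient, whereas the objective is about patients who are recommended a change. If the message alone counted, almost every CNNF patient with a delivered message would score positive, and the endpoint would duplicate the fidelity measure.

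**When.** The objective's timing is compatible with a chart review that begins in week 7. The adherence endpoint and the fidelity text in 7.2.1 both place a chart review at week 7-10. These are dates of review. No text states between which dates a recommendation must be recorded, so that detail is open. Section 5.2 gives controls the strategy at study completion, and 5.4 puts patient completion after week 25, which on its face is later than the last review marked in the schedule. The synopsis gives a participant duration of 10 weeks, so this reassurance is partial. The week 7-10 review is the natural source for the endpoint.

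**Schedule label.** The row in 1.3 does not say that chart review serves exploratory outcomes only. Section 9.3 assigns secondary endpoints to chart review, and the synopsis says endpoints will also be assessed that way. The label is incomplete.

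**Masking.** The documents do not say that abstraction is masked or that it is unmasked. Section 7.2.1 checks fidelity at the week 7-10 review, which makes unmasked review plausible, but this is an inference.

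**Size.** The plan sizes only the primary endpoint. Its inputs (section 11.1) are 5% versus 35%, two-sided 5%, 90% power, mean cluster size 2, CV 0.62 and ICC 0.95.

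- Per arm before clustering: (1.960 + 1.282)² × (0.05×0.95 + 0.35×0.65) / 0.30² = 32.1, rounded up to 33.
- Design effect: 1 + ((0.62² + 1)×2 − 1)×0.95 = 2.680.
- 33 × 2.680 = 88.5 patients, or 44.2 clinicians, per arm; 176.9 in total, against the plan's 44 and 176. Then 176/0.8 = 220.

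The sample size reproduces and does not depend on this point.

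For the secondary endpoint, an illustration needs assumptions that are not in the documents: no true difference, a share f of otherwise negative CNNF patients scored positive only from CNNF paperwork, and the primary design effect, so that effective n = 110/2.680 = 41.0 per arm. The CNNF rate becomes base + f(1 − base); for example, 0.05 + 0.10×0.95 = 0.145.

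| True rate in both arms | f = 5% | f = 10% | f = 20% | f = 30% |
|---|---|---|---|---|
| 5% | 13% | 30% | 69% | 92% |
| 20% | 6% | 13% | 36% | 65% |

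Entries are the chance of a significant result favouring CNNF; with correct scoring it would be 2.5%. The table shows what systematic misreading would cost. It is not evidence that any will occur.

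**The case for a change.** The strongest case for acting is that the protocol is precise where it chooses to be: the primary endpoint has a source, day counts and a window, and an exploratory endpoint names the clinician and the review week. The sole secondary endpoint has less. The ambiguity lies in one arm, no sentence excludes the message, and even modest misscoring could produce a false positive, as the table shows. A few added words would cost nothing.

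Part of this stands. The endpoint sentence is terse, the recording dates are unstated, abstractor masking is unstated and the schedule label is incomplete. But each remedy would only write down a definition, a status or a label; none alters the design, the data collected or the analysis. The table depends wholly on assumed misclassification shares and true rates and on a borrowed design effect. The reading it guards against conflicts with the plan's own list of separate endpoints. Asking the plan to declare abstraction unmasked would go beyond the text. Fixing the window as study entry to the chart review would let follow-up vary with the day each chart is opened, which is not clearly better than the present wording.

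**Conclusion.** No change to the plan follows. On who recommends, this is a gap that analysts fill sensibly: related text points consistently to the clinician's decision. On the schedule row, it is a clerical slip that section 9.3 resolves. The recording dates and abstractor masking are open details that an abstraction form can settle, with the same dates in both arms, and that the trial report can describe.

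The scope is one secondary endpoint in 220 planned patients. No bias is shown and none can be computed from the documents. The primary endpoint comes from patient self-report, and the stated 44 clinicians per arm, 176 and 220 are unaffected. The conclusion assumes that abstractors do not count the CNNF message by itself and that the endpoint is taken from the week 7-10 review. If either proved false, the secondary comparison would need to be read with caution; the primary result would not.
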